#### 5.2.2.2 Adverse event collection and reporting

##### AE collection

Upon enrolment into a trial, the subject's baseline condition is assessed (for instance, by documentation of medical history/concomitant diagnoses), and relevant changes from baseline are noted subsequently.

Subjects will be required to report spontaneously any AEs as well as the time of onset, end, and intensity of these events. In addition, each subject will be regularly assessed by the medical staff throughout the clinical trial and whenever the investigator deems necessary. As a minimum, subjects will be questioned for AEs (and concomitant therapies) at the time points indicated in the [Flow Chart](#). Assessment will be made using non-specific questions such as 'How do you feel?'. Specific questions will be asked wherever necessary in order to more precisely describe an AE.

A carefully written record of all AEs shall be kept by the investigator in charge of the trial. Records of AEs shall include data on the time of onset, end time, intensity of the event, and any treatment or action required for the event and its outcome.

The following must be collected and documented on the appropriate CRF(s) by the investigator:

- From signing the informed consent onwards until an individual subject's end of trial:
  - All AEs (serious and non-serious) and all AESIs
  - The only exception to this rule are AEs (serious and non-serious) and AESIs in Phase I trials in healthy volunteers, when subjects discontinue from the trial due to screening failures prior to administration of any trial medication. In these cases, the subjects' data must be collected at trial site but will not be entered in the CRF or trial database and will not be reported in the CTR.

- After the individual subject's end of trial:
  - The investigator does not need to actively monitor the subject for new AEs but should only report any occurrence of cancer and related SAEs and related AESIs of which the investigator may become aware of by any means of communication, e.g. phone call. Those AEs should, however, not be reported in the CRF.

The REP for BI 730460, the time interval when measurable drug levels or PD effects are still likely to be present after last administration, is not known for this first-in-human trial at this early stage of development. Therefore, all AEs reported until the end of trial examination (last per protocol contact) will be considered on treatment; please see Section [7.3.3](#).

### **AE reporting to the sponsor and timelines**

The Investigator must report SAEs, AESIs, and non-serious AEs which are relevant for the reported SAE or AESI, on the BI SAE form via fax immediately (within 24 hours) to the sponsor's unique entry point (country specific contact details will be provided in the ISF). The same timeline applies if follow-up information becomes available. In specific occasions the Investigator could inform the sponsor upfront via telephone. This does not replace the requirement to complete and fax the BI SAE form.

With receipt of any further information to these events, a follow-up SAE form has to be provided. For follow-up information, the same rules and timeline apply as for initial information.

### **Information required**

For each AE, the investigator should provide the information requested on the appropriate eCRF pages and the BI SAE form, if applicable.

All (S)AEs, including those persisting after the individual subject's end of trial, must be followed up until they have resolved, have been assessed as 'chronic' or 'stable', or no further information can be obtained.

### **5.2.3 Assessment of safety laboratory parameters**

For the assessment of laboratory parameters, blood and urine samples will be collected by the trial site at the time points indicated in the [Flow Chart](#) after the subjects have fasted for at least 10 h (excluding 4-hour post-dose sample). Overnight fasting is not required at the discretion of the Investigator or designee for retests.

The parameters that will be determined are listed in Tables [5.2.3: 1](#) and [5.2.3: 2](#). Reference ranges will be provided in the ISF, Section 10.

Manual differential white blood cell count or urine sediment examinations will only be performed if there is an abnormality in the automatic blood cell count or in the urinalysis, respectively.

Table 5.2.3: 1 Routine laboratory tests

Functional lab group	Test name	A 	B 	C 	D 
Haematology	Haematocrit	X	X	X	X
	Haemoglobin	X	X	X	X
	Red blood cells (RBC)	X	X	X	X
	White blood cells (WBC)	X	X	X	X
	Platelets	X	X	X	X
	Reticulocyte count	X	X	X	X
Automatic WBC differential (relative and absolute)	Neutrophils	X	X	X	X
	Eosinophils	X	X	X	X
	Basophils	X	X	X	X
	Monocytes	X	X	X	X
	Lymphocytes	X	X	X	X
Manual differential WBC (if automatic differential WBC is abnormal)	Polymorphnuclear neutrophils (segs), band neutrophils (stabs), eosinophils, basophils, monocytes, lymphocytes				
Coagulation	Activated partial thromboplastin time (aPTT)	X	X	--	X
	Prothrombin Time (Quick and INR)	X	X	--	X
Enzymes	Aspartate aminotransferase (AST/GOT)	X	X	--	X
	Alanine aminotransferase (ALT/GPT)	X	X	--	X
	Alkaline phosphatase (AP)	X	X	--	X
	Gammaglutamyl transferase (GGT)	X	X	--	X
	Lactate dehydrogenase	X	X	--	X
	Lipase	X	--	--	X
Electrolytes	Calcium	X	X	--	X
	Sodium	X	X	--	X
	Potassium	X	X	--	X
Substrates	Plasma glucose	X	X	--	X
	Creatinine	X	X	--	X
	Total bilirubin	X	X	--	X
	Direct bilirubin	X	X	--	X
	Total protein	X	X	--	X
	C-Reactive Protein (CRP)	X	X	--	X
	Urea in serum	X	X	--	X
	Phosphate in serum	X	X	--	X
	Total cholesterol	X	X	--	X
	Triglycerides	X	--	--	X
Hormones	Thyroid stimulating hormone (TSH)	X	--	--	--

 A: parameters to be determined at visit 1 (screening examination)

 B: parameters to be determined at visits 2 and 3 on Days -3 to -1 and Days 1 to 4 (for time points, refer to [Flow Chart](#))

 C: parameters to be determined at visits 2 and 3 on Day 8 (for time point, refer to Flow Chart)

 D: parameters to be determined at visit 4 (end of trial examination)

Table 5.2.3: 1 Routine laboratory tests (cont.)

Functional lab group	Test name	A 	B 	C 	D 
Urinalysis (Stix)	Urine nitrite	X	X	--	X
	Urine protein	X	X	--	X
	Urine glucose	X	X	--	X
	Urine ketone	X	X	--	X
	Urobilinogen	X	X	--	X
	Urine bilirubin	X	X	--	X
	Urine RBC	X	X	--	X
	Urine WBC	X	X	--	X
	Urine pH	X	X	--	X
Urine sediment (microscopic examination if erythrocytes, leukocytes nitrite or protein are abnormal in urine)	Only positive findings will be reported (e.g. presence of sediment bacteria, casts in sediment, squamous epithelial cells, erythrocytes, leukocytes)			--	

 A: parameters to be determined at visit 1 (screening examination)

 B: parameters to be determined at visits 2 and 3 on Days -3 to -1 and Days 1 to 4 (for time points, refer to [Flow Chart](#))

 C: parameters to be determined at visits 2 and 3 on Day 8 (for time point, refer to Flow Chart)

 D: parameters to be determined at visit 4 (end of trial examination)

The tests listed in Table 5.2.3: 2 are exclusionary laboratory tests that may be repeated as required. The results will not be entered in the CRF/database and will not be reported in the CTR. Except for drug screening, it is planned to perform these tests at screening only. Drug screening will be performed at screening and prior to each administration of trial medication on Day 1 (for time points refer to Flow Chart).

Table 5.2.3: 2 Exclusionary laboratory tests

Functional lab group	Test name
Drug screening (urine)	Amphetamine/MDA
	Barbiturates
	Benzodiazepine
	Cannabis
	Cocaine
	Methadone
	Methamphetamines/MDMA/XTC
	Opiates
	Phencyclidine
	Tricyclic antidepressants
Infectious serology (blood)	Hepatitis B surface antigen (qualitative)
	Hepatitis B core antibody (qualitative)
	Hepatitis C antibodies (qualitative)
	HIV-1 and HIV-2 antibody (qualitative)
	Interferon-γ release assay to tuberculosis (qualitative), e.g. QuantiFERON ® -TB Gold Test

To encourage compliance with alcoholic restrictions, a breath alcohol test (Alcotest® 7410, Dräger AG, Lübeck, Germany) will be performed prior to each treatment period at time

points indicated in the [Flow Chart](#), and may be repeated at any time during the study at the discretion of an investigator or designee. The results will not be included in the CTR.

The laboratory tests listed in Table [5.2.3: 1](#) and [5.2.3: 2](#) will be performed at MVZ Labor Ravensburg GbR, [name] with the exception of the drug screening tests. Drug screening will be performed at the trial site using M-10/14-PDT Multiline test or comparable tests.

Laboratory data will be transmitted electronically from the laboratory to the trial site.

## **5.2.4      Electrocardiogram**

### **5.2.4.1      12-lead resting ECG**

#### Recording

Twelve-lead resting ECGs (I, II, III, aVR, aVL, aVF, V1 - V6) will be recorded using a computerised electrocardiograph (CardioSoft EKG System, GE Medical Systems, Freiburg, Germany) at the time points given in the Flow Chart. Electrode placement will be performed according to the method of Wilson, Goldberger and Einthoven modified by Mason and Likar (hips and shoulders instead of ankles and wrists). Precise electrode placement will be marked with an indelible mark on the skin to allow reproducible placement throughout the study.

To achieve a stable heart rate at rest and to assure high quality recordings, the site personnel will be instructed to assure a relaxed and quiet environment so that all subjects are at complete rest.

All ECGs will be recorded for a 10-sec duration after subjects have rested for at least 5 min in a supine position. ECG recording will always precede all other study procedures scheduled for the same time (except for blood drawing from an intravenous cannula that is already in place) to avoid compromising ECG quality.

ECGs will be recorded as single ECGs or as triplicate ECGs (i.e. three single ECGs recorded within 180 sec) as indicated in the Flow Chart.

ECGs may be repeated for quality reasons for instance due to alternating current artefacts, muscle movements, or electrode dislocation. For repetition within triplicate ECGs the time window of 180 sec applies as well. The repeat ECGs are assigned to the respective scheduled time point.

Additional (unscheduled) ECGs may be recorded for safety reasons. These ECGs are assigned to the prior scheduled time point in the sponsor's database.

#### Storing

All ECGs will be stored electronically on the Muse Cardiology Information System (GE Medical Systems, Freiburg, Germany).

#### Data transfer

For time points specified in the Flow Chart, ECGs will be transferred electronically to a central ECG lab ( ) for evaluation.

In case of repeat ECGs due to quality reasons, only the repeated ECG recordings will be transferred to the central ECG lab, whereas the initially recorded ECGs will be discarded. Unscheduled ECGs (for safety reasons) will be transferred to the central ECG lab but will not be included into the statistical analysis of interval lengths.

Data transfer from the central ECG lab to the sponsor is described in the ECG data transfer agreement (see TMF).

### Evaluation

#### a) Central ECG lab (SRD part only)

For the SRD part, central ECG lab evaluation will be performed post-study for the first of three replicate ECGs per time point on Days 1, 2 and 3. For baseline, where 3 triplicate ECGs are recorded, only the first triplicate ECG (i.e. 3 single ECGs) will be evaluated. This will include the determination of cardiac QRS-axis as assessed by the ECG machine's algorithm as well as the intervals RR, PR, QRS and QT measured semi-automatically. The remaining second and third replicate ECG will be stored for additional analysis if required, e.g. by authorities at a later time point.

Heart rate (HR) and the QT interval corrected for HR (QTc e.g. QTcF and QTcB) will be determined by the sponsor (see TSAP for details).

All semi-automatic interval measurements in one subject will be performed on the same lead. The intervals will be measured from four cardiac cycles (beats) in lead II. If lead II shows a flat T wave or is not measurable for any reason, lead V5 will be used, or if that lead is not measurable, then lead I will be used. The lead actually used will be reported in the CTR. For automatic interval measurements no lead will be provided

For blinding arrangements see Section [4.1.5.1](#). No more than two blinded readers will evaluate all ECGs of the study. ECGs from a particular subject should be evaluated by a single reader.

Evaluation of ECGs will comply with the ICH E14 guidance document and supplements [R07-4722, R16-0366] as well as the FDA requirements for annotated digital ECGs [[R09-4830](#)].

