2. The time is approximate; the respective procedure is to be performed and completed within 3 h prior to drug administration. Allocation to treatment may be performed at any time following enrolment but must be completed prior to (first) drug administration.
3. If several actions are indicated at the same time point, the intake of meals will be the last action.
4. End of trial examination includes physical examination, vital signs, ECG, safety laboratory, recording of AEs and concomitant therapies.
5. Only urine drug screening and alcohol breath test will be done at this time point.
6. AEs and concomitant therapies will be recorded throughout the trial, but will be specifically asked for at the time points indicated in the Flow Chart above.

7. Safety laboratory to be taken and to be medically evaluated within 3 days prior to administration of study drug; this ambulatory visit including the safety laboratory can be omitted, if the screening examination is performed on Days -3, -2 or -1.
  8. Two blood sample for stability testing will be taken at this time point (refer to Section [5.5.2.4](#))
  9. The ECG recording has to be performed as triplicate at this time point
  10. Sampling times and periods may be adapted based on information obtained during the trial (e.g. preliminary PK data) including addition of samples and visits as long as the total blood volume taken does not exceed 500 mL per subject
- 
13. Two blood samples should be collected: 4.3 mL in sodium citrate tubes and 4.5 mL in lithium heparin tubes.
  14. The ECG will be recorded as single ECG at this time point
  15. At baseline (i.e. Day 1, prior to drug administration) 3 triplicate ECGs are recorded within approximately one hour. The recordings of each first triplicate ECG should be separated by at least 15 minutes.
  16. Only haematology with automatic WBC differential (refer to Table [5.2.3: 1](#)) at this time point.

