6.6 HANDLING OF MISSING DATA AND OUTLIERS

Handling of missing data and outliers will be performed as described in the CTP, Section 7.4.

The only exceptions where imputation might be necessary for safety evaluation are AE dates. Missing or incomplete AE dates are imputed according to BI standards (see 001-MCG-156_RD-01 (4)).

Missing data and outliers of PK data are handled according to BI standards (see 001-MCS-36-472_RD-01) (5).

If single cardiac cycles of an ECG (out of the generally four) are missing, the arithmetic mean for this single ECG will be computed with the reduced (1, 2 or 3) number of cardiac cycles.

If replicate ECG recordings are missing, the arithmetic means per time point will be computed with the reduced number (1 or 2) of recordings.

For the classification of the on treatment QTc/QT intervals into “no new onset” / “new onset” categories, a missing value is obtained only in case that

- (i) all on treatment values are missing and
- (ii) the baseline value is less than or equal to 500 msec, or missing.

If condition (i) is fulfilled but the baseline value is greater than 500 msec, this case will be categorized as ‘no new onset’. If baseline is missing and the maximum on treatment QTc interval is greater than 450 msec (or 500 msec for QT interval, respectively), this is classified as a ‘new onset’ in the respective category. If baseline is missing and the maximum QTc interval is less than or equal to 450 msec (or 500 msec for QT interval, respectively), this will be categorized as ‘no new onset’. If baseline is missing, a QTc/QT interval > 500 msec at any time on treatment will be a notable finding.

For placebo subjects, the missing plasma concentration values will be replaced by 0 for the exposure-response analyses. For subjects on active drug, missing plasma concentration values with ‘BLQ’ in the comment field will be replaced by ½ LLOQ.

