At Visit 2, triple ECGs will be recorded (three single ECGs within 180 sec).

Prior to study drug administration, 3 triplicate ECGs (9 single ECGs) will be recorded. The vendor will analyse the first single ECG per triplicate for all on treatment timepoints.

The baseline value of an ECG variable is defined as the mean of the first triplicate ECG measurement at -01:30 prior to drug administration.

Section 5.2.4.1 of the CTP: *For the SRD part, central ECG lab evaluation will be performed post-study for the first of three replicate ECGs per time point on Days 1, 2 and 3. For baseline, where 3 triplicate ECGs are recorded, only the first triplicate ECG (i.e. 3 single ECGs) will be evaluated. This will include the determination of cardiac QRS-axis as assessed by the ECG machine's algorithm as well as the intervals RR, PR, QRS and QT measured*

semi-automatically. The remaining second and third replicate ECG will be stored for additional analysis if required, e.g. by authorities at a later time point.

For the exposure response analyses, pairs of ECG variables and corresponding plasma concentrations will be built using the same planned time points, e.g. HR change from baseline and the plasma concentration measured at planned time 1:00 will build one pair. Whether a time deviation between PK blood sampling time and corresponding ECG recording is too big and the pair has to be excluded from the analysis will be decided no later than at the RPM. This critical time deviation depends on the PK properties. When plasma concentrations are expected to change only little around a given time point, the acceptable time deviation between ECG recording and PK blood sampling may be bigger.

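### The ECG baseline text uses only the -1:30 triplicate, while SAP Table 6.7: 1 schedules central reads at all three predose times; the single-window definition is never more precise and has no fallback

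*Protocol*

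**What the plan says.** The SRD flow chart (footnote 15) provides for repeated predose recording: "At baseline (i.e. Day 1, prior to drug administration) 3 triplicate ECGs are recorded within approximately one hour", and "The recordings of each first triplicate ECG should be separated by at least 15 minutes". SAP 6.7 gives the count: "Prior to study drug administration, 3 triplicate ECGs (9 single ECGs) will be recorded". Protocol 5.2.4.1 describes "triplicate ECGs (i.e. three single ECGs recorded within 180 sec", so one triplicate covers at most three minutes.

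Four places then bear on which recordings form the baseline:

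- Protocol 5.2.4.1, central ECG lab: "For baseline, where 3 triplicate ECGs are recorded, only the first triplicate ECG (i.e. 3 single ECGs) will be evaluated".
- SAP 6.7, text: "The baseline value of an ECG variable is defined as the mean of the first triplicate ECG measurement at -01:30 prior to drug administration". After dosing, "The vendor will analyse the first single ECG per triplicate for all on treatment timepoints".
- SAP Table 6.7: 1: the first of three replicates is centrally evaluated at -1:30, -1:15 and -1:00.
- Protocol 7.3.3: baseline is the mean of the predose triplicate measurements, without saying whether one triplicate or all three are meant.

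SAP 6.7 also opens with a general rule that baseline is the last value before dosing. For ECGs the specific rule follows it.

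On missing data, SAP 6.6 averages the one or two replicates that remain at a time point. It also has rules for a wholly missing baseline, including one that begins "If baseline is missing and the maximum on treatment QTc interval is greater than 450 msec" and classes the subject as a new onset. No rule turns to the other predose triplicates.

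**The concern.** The passages do not give one reading plan. The SAP text needs three reads at -1:30. The SAP table supplies one read there and one at each of the two later times. A programmer and the ECG laboratory could each follow a different instruction.

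If the text is followed, the spacing of the predose recordings is lost for the baseline. Averaging within three minutes reduces replicate noise but leaves the subject's variation from one occasion to the next. The same baseline value enters every change from baseline in QTcF, HR, QT, PR and QRS, the new-onset classes, and both the response and the baseline covariate of the concentration-QTcF and concentration-HR models. Its error is common to all 12 on-treatment values of a subject, so averaging over time points does not remove it. At the planned 2 per group, six dose groups give 12 placebo subjects, so a between-group comparison feels that error.

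The single window also has no substitute. A subject whose -1:30 triplicate is wholly unusable has no change from baseline, even with six further predose ECGs on file. One active subject is 1 of 6 in a dose group.

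**Working it through.** The documents state no SD, precision or power for any ECG endpoint, so there is no planned figure to reproduce.

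**Inputs from the documents.** Three predose windows of three ECGs (9 in all); one central read at each of 12 on-treatment times; six dose groups of 6 active and 2 placebo, giving 36 and 12.

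**Assumed inputs.** Between-subject SD 15 ms, between-occasion SD sb = 6 ms, within-triplicate SD sw = 4 ms, and correlation rho between predose occasions of 0, 0.5 or 0.8.

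**Step 1, baseline error variance v.**

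- Three reads in one window: v = sb² + sw²/3.
- One read in each of three windows: v = sb²(1+2rho)/3 + sw²/3.

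The difference is sb² × 2(1-rho)/3. It is never negative, and it is positive whenever sb > 0 and rho < 1. The direction therefore needs no assumed SD.

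**Step 2, change from baseline for one subject at one time**, as in the descriptive tables, taking the post-dose read as independent of the predose occasions: SD = √(sb² + sw² + v) = √(52 + v).

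**Step 3, SE of the active-placebo intercept after adjustment for baseline.** Residual between-subject variance R = 225 × v/(225 + v). SE = √[(R + 52/12) × (1/36 + 1/12)], where 1/36 + 1/12 = 1/9.

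| Reads | v (ms²) | Baseline error SD (ms) | SD of change (ms) | R (ms²) | SE of intercept (ms) | SE reduction |
|---|---|---|---|---|---|---|
| All at -1:30 | 36 + 5.33 = 41.33 | 6.4 | 9.66 | 34.92 | 2.09 | – |
| Spread, rho 0 | 12 + 5.33 = 17.33 | 4.2 | 8.33 | 16.09 | 1.51 | 28% |
| Spread, rho 0.5 | 24 + 5.33 = 29.33 | 5.4 | 9.02 | 25.95 | 1.83 | 12% |
| Spread, rho 0.8 | 31.2 + 5.33 = 36.53 | 6.0 | 9.41 | 31.43 | 1.99 | 5% |

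**Step 4, sensitivity to the variance split.** The SDs above put 36/52 = 69% of within-subject variance between occasions. For other shares, the SD of an individual change under the single-window definition, relative to spread reads, is:

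| Between-occasion share | rho 0 | rho 0.5 |
|---|---|---|
| 0 | 1.000 | 1.000 |
| 0.25 | 1.061 | 1.029 |
| 0.5 | 1.118 | 1.054 |
| 1 | 1.225 | 1.095 |

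**Step 5, the planned concentration model.** SAP 7.8.4 has a baseline covariate and a random intercept and slope, and targets the BI-placebo difference at the geometric mean Cmax. I took the 200 mg value of 1,864 nM from SAP Section 4. I assumed a plasma profile with the 14 h half-life anticipated in Protocol 2.3 and a random-slope SD of 2 ms/µM. The generalised least squares SE of that difference is about 3.10 ms as worded, against 2.59, 2.90 or 3.00 ms for rho 0, 0.5 or 0.8. The reductions are about 16%, 6% and 3%.

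**Step 6, loss of the window.** Suppose each of 48 subjects independently has a chance p that the whole -1:30 triplicate is unusable. The chance of at least one subject without a baseline is 1 - (1-p)^48: 0.38 at p = 1% and 0.62 at p = 2%. If any one of three windows sufficed, and windows failed independently, it would be 1 - (1-p³)^48, below 0.001 in both cases.

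**The case against.** The strongest reply is that this is mainly an inconsistency, with a precision argument of unknown size attached. No ECG variance or correlation is in the documents. Occasions 15 minutes apart may be highly correlated, and at rho 0.8 the gain in the intercept SE is 0.1 ms. The concentration-QTcF analysis is exploratory, and ECG intervals are neither primary nor secondary endpoints. All of that stands, and it limits the importance of the point. It does not reverse the direction or supply the missing fallback.

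The missing-baseline case is also narrow. One or two remaining replicates are averaged, repeats for quality are allowed within the 180 seconds, and the missing-baseline rule errs towards flagging. Subjects with QTc repeatedly above 450 ms at screening are excluded. This stands too: the gap arises only if the whole triplicate fails, and the probabilities in step 6 rest on an assumed p.

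Finally, the SAP was written after the trial stopped at 200 mg, and Protocol 4.1.5.1 has the database handled open-label, so a new baseline could look data-driven. That is a reason to decide without sight of on-treatment ECG results, not a reason to leave the conflict. The ECGs are stored electronically and central reading is post-study, so the choice of reads can still be settled or supplemented.

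**Conclusion.** The point holds. Protocol 5.2.4.1 and the SAP 6.7 text place the baseline in one three-minute window; SAP Table 6.7: 1 schedules a different set of reads, and Protocol 7.3.3 is open. For the same three reads, one per window is never less precise. The size is not known from the documents. On the assumed 6 and 4 ms, the intercept SE falls by 5% to 28%, and the SE of the difference at Cmax in the random-slope model by about 3% to 16%. Without between-occasion variation the gain is nil. The model details in SAP 9.3 are not in the public text, so the random-slope figures follow the SAP 7.8.4 description only.

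A reader might infer more than this, without support:

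- *The later predose ECGs are never used.* They are left out of the baseline as the SAP text defines it. Table 6.7: 1 nevertheless schedules central reads of them, the site evaluates all local ECGs, and unread replicates are stored.
- *The ECG results are biased.* The extra error widens intervals; nothing shows that it shifts the BI-placebo difference.
- *Any subject with a defective -1:30 recording lacks a baseline.* All three replicates must be unusable.
- *The loss is 28%.* That figure needs uncorrelated occasions and the assumed SDs.

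**What to change.** Reconcile Protocol 5.2.4.1, Protocol 7.3.3, the SAP 6.7 text and Table 6.7: 1 with one definition: the ECG baseline is the mean of the centrally read first replicates at -1:30, -1:15 and -1:00, as the table already schedules. If one is missing, average those available. Apply the missing-baseline rules of SAP 6.6 only when no predose ECG can be evaluated. Say that this replaces the general last-value rule for ECG variables.

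Record the change and its reason in SAP Section 4, and make the decision without reference to on-treatment ECG results.

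The cost is wording, with no new recordings. The total stays at three central baseline reads per subject if predose reading has not begun; the documents do not say whether it has. If the -1:30 triplicate has already been read, up to two further reads per subject are needed. The drawback is a baseline that differs from the one now worded.
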